11.2.1	General Approach	28
11.2.2	Primary & Secondary Endpoints	29
11.2.3	Other Pre-specified Analyses	29
12	Interim Analysis	30
13	Publications	30
14	protocol amendment history	30

STATEMENT OF COMPLIANCE

The trial will be carried out in accordance with International Conference on Harmonisation Good Clinical Practice (ICH GCP) and the following:

- United States (US) Code of Federal Regulations (CFR) applicable to clinical studies (45 CFR Part 46, 21 CFR Part 50, 21 CFR Part 56, 21 CFR Part 312, and/or 21 CFR Part 812)

National Institutes of Health (NIH)-funded investigators and clinical trial site staff who are responsible for the conduct, management, or oversight of NIH-funded clinical trials have

completed Human Subjects Protection and ICH GCP Training.

The protocol, informed consent form(s), recruitment materials, and all participant materials will be submitted to the Institutional Review Board (IRB) for review and approval. Approval of both the protocol and the consent form must be obtained before any participant is enrolled. Any amendment to the protocol will require review and approval by the IRB before the changes are implemented to the study. In addition, all changes to the consent form will be IRB-approved; a determination will be made regarding whether a new consent needs to be obtained from participants who provided consent, using a previously approved consent form.

PROTOCOL SUMMARY^{CT.GOV}

Title:

A pilot and feasibility study of a chronic pain self-management intervention for older adults incorporating podcasts and patient priorities.

Study Description:

This randomized pilot trial tests the feasibility of a community health worker (CHW)-delivered chronic pain self-management intervention for older adults ("STEP-UP"; Support, Training, and Education for Pain Self-Management – Using Podcasts) in a primary care setting.

Objectives*:

We will conduct a randomized (waitlist) pilot trial (n=40) in a Federally Qualified Health Center.

Endpoints*:

Primary Endpoint: Improvement in pain interference at 8 weeks (post-program)
Secondary Endpoints: physical functioning and global impression of change, and participant engagement and satisfaction (secondary outcomes) at 8 weeks

Study Population:

We will recruit 40 adults from a FQHC who are age 50+ with high-impact chronic pain.

Phase* or Stage:

Stage 1 (Behavioral Stage Model) Pilot Trial

**Description of Sites/Facilities
Enrolling Participants:**

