1.3 Specific Aims

1. Develop and beta-test the STEP-UP chronic pain self-management intervention.
 - a) Create podcast episodes based on content from our existing STEPS and Positive STEPS CPSM interventions and lessons learned from podcast production in our ongoing RESET study.
 - b) Design community health worker session protocols and adapt the PPC process for the pain care context with expert and provider input.
 - c) Conduct a “beta” test of STEP-UP (n=5 participants) to refine content and processes.
2. Conduct a pilot RCT of STEP-UP.

- a) Using a waitlist randomized control design, deliver the STEP-UP intervention to 40 adults, age 50+ with high-impact chronic musculoskeletal pain, in a Federally-Qualified Health Center.
- b) Assess baseline to post-program changes in pain interference (primary outcome) and global impression of change in pain and functioning and participant engagement (secondary outcomes). Use mixed methods to evaluate key processes and explore mechanisms of effect.

Conduct qualitative interviews with clinic providers and administrators to: 1) identify factors affecting implementation, and 2) assess needs regarding a future provider-facing STEP-UP component. **JAN 11, 2023, NOTE: This will follow the pilot trial and the sampling plan will be informed by our experience during the trial; therefore, we will seek IRB approval for this element at a later date. ***

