2 OBJECTIVES & ENDPOINTS

OBJECTIVES	ENDPOINTS	JUSTIFICATION FOR ENDPOINTS
Primary		
To determine if participating in the STEP-UP intervention leads to decreased pain interference with daily functioning.	PROMIS Pain Interference 6a scale is the primary endpoint (pain interference is assessed at baseline, and 8 weeks from baseline). A 2.5 point difference in T-score is considered clinically significant.	Pain interference is a patient-centered outcome that indicates pain's impact on valued and necessary activities. This intervention teaches skills such as goal setting to gradually increase engagement in daily activities.
Secondary		
To determine if participating in the STEP-UP intervention leads to greater improvement in Global Impression of Change in Pain and Functioning.	Patient Global Perception of Change since baseline will be assessed at 8 weeks. Participants will be asked about pain and functioning in separate items.	“Global impression of change” variables capture participants’ subjective perceptions of intervention benefit.

To assess participant engagement in the intervention.	Number of sessions (out of 7) completed at 8 weeks from baseline.	Given the novel nature of this intervention and the barriers that many participants may experience to engagement, it is important to assess whether the intervention as designed yields acceptable engagement levels.
To assess participant satisfaction with the intervention.	Items ask about overall satisfaction with the program, e.g., whether participation increased understanding of pain management (1= Strongly Disagree to 5= Strongly Agree). A higher score indicates higher patient satisfaction.	These items will facilitate understanding of the intervention's acceptability in the priority population as well as highlight potential areas for improvement prior to a larger trial or another future iteration of the intervention.

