11.2.2 Primary & Secondary Endpoints

We will calculate baseline descriptive statistics and compare groups using independent-sample t-tests for continuous variables and chi-squared tests for categorical variables. We will assess psychometrics of scales used (e.g., internal consistency reliability and concurrent validity). We will convert the PROMIS 6-item Pain Interference subscale score to T-scores (a standardized score with a mean of 50 and SD of 10) by summing the scales and using the conversion tables provided at HealthMeasures.net.

To assess the effect of being in the intervention group, we will use a univariate analysis of variance model for continuous primary and secondary outcomes. The dependent variable in each model will be the value of the outcome at 8-week follow-up; the independent factor will be treatment group (intervention vs. control), with the baseline value of the outcome as a covariate.

Effect size will be indicated by partial eta squared for the treatment group variable. In order to assess the potential clinical relevance of the intervention, we will use chi-squared tests to compare the percentage of participants in each treatment condition who achieved the Minimally Important Difference (MID) of ≥ 3 T-score points in PROMIS pain interference.

We will repeat this analysis with the secondary outcomes: Global Impression of Change in Pain and Functioning. Transformations for non-normality of outcomes will be performed as indicated.

We will also assess the moderating effect of selected variables such as sex, age, baseline pain intensity, and degree of program engagement. Moderation analyses will use standard approaches to evaluate interactions between these covariates and treatment group.

For patient engagement, the secondary outcome indicating feasibility that is composed of: 1) number of sessions completed out of 7; and 2) participant satisfaction on a 5-point Likert scale, we will calculate descriptive statistics. We will also explore differences by age group (under 65/65+) as well as gender. As an exploratory analysis, we will investigate whether satisfaction differs according to whether or not participants achieved the MID on the primary outcome of pain interference.

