11.2.3 Other Pre-specified Analyses

To explore potential mechanisms, we will examine the association between: 1) participation in the intervention and the hypothesized composite mediator, Perceived Control Over Pain, as well as each of the 4 component scales (Survey of Pain Attitudes Control subscale, Pain Catastrophizing Scale, Life Control scale, and PROMIS Meaning and Purpose); and 2) between mediators and outcomes. Positive correlations in both cases will provide evidence for a potential mediating effect.

Following intent-to-treat principles, we will include all participants randomized to the intervention group, with sensitivity analyses assessing whether different levels of participant engagement (i.e., session completion) impact results.

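### The mediation criterion in 11.2.3 (two positive correlations) has the wrong sign for pain interference, where lower is better and no recoding is stated

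*Combined protocol and SAP*

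**What the plan says.** Section 11.2.3 examines two associations: between participation and the mediators, and "between mediators and outcomes". The mediators are a composite, Perceived Control Over Pain, and each of its four components taken separately: "Survey of Pain Attitudes Control subscale, Pain Catastrophizing Scale, Life Control scale, and PROMIS Meaning and Purpose". The section then gives its one criterion: "Positive correlations in both cases will provide evidence for a potential mediating effect". It states no scoring direction for any mediator, no recoding of any outcome, and no exemption for the primary outcome.

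The primary objective in Section 2 is "To determine if participating in the STEP-UP intervention leads to decreased pain interference with daily functioning", so a lower score is the favourable result. On scoring, Section 11.2.2 says "We will convert the PROMIS 6-item Pain Interference subscale score to T-scores" and mentions no reversal.

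Other sections describe the outcome in other ways. Aim 2b in Section 1.3 speaks of changes from baseline to after the program. The Protocol Summary words the primary endpoint as an improvement. Section 11.2.2 also compares the percentages of participants who reach the minimally important difference (MID). None of these is tied to the mediation analysis.

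**The concern.** The criterion suits a mediator and an outcome that are both scored so that higher is better. Pain interference runs the other way. If the intervention raises perceived control and greater control lowers pain interference, the first correlation is positive and the second is negative. Two positives would mean that the intervention raises something that goes with more interference.

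Pain Catastrophizing adds a second difficulty. It appears to run opposite to the other three scales, yet it is tested alone under the same criterion.

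Aim 2b includes the intention to "explore mechanisms of effect". Applied literally to the T-score, the criterion would credit a mediator that works against benefit and would not recognise one that works as hypothesised. If the signs are not fixed in advance, they will have to be settled later, possibly after the data have been seen.

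**Working it through.** The plan gives no figure on this point to reproduce. The check is one of signs and needs no effect sizes.

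**Inputs**
- Criterion, mediators and outcomes: Section 11.2.3.
- Favourable direction of pain interference, a decrease: Section 2.
- Possible codings of pain interference: T-score at 8 weeks (11.2.2), change from baseline (1.3), improvement (Protocol Summary), MID achieved (11.2.2).
- Assumed, because the documents do not give scoring directions: higher is favourable for SOPA Control, Life Control and Meaning and Purpose (the control-type scales), and higher is unfavourable for Pain Catastrophizing. Both are read from the scale names.

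**Formula**

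Let s = +1 if a higher mediator score is favourable and −1 if not. Let o = +1 if a higher outcome score is favourable and −1 if not. For a mechanism that works as hypothesised:
- sign of participation–mediator = s
- sign of mediator–outcome = s × o
- product of the two signs = s × s × o = o

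So the two signs agree only if o = +1, and both are positive only if s = +1 as well.

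**Results**

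| Coding of pain interference | o | Control-type scales (s = +1) | Pain Catastrophizing, unreversed (s = −1) | Scales with both signs positive | Same, Pain Catastrophizing reversed |
|---|---|---|---|---|---|
| T-score at 8 weeks | −1 | + / − | − / + | 0 of 4 | 0 of 4 |
| Raw change, 8-week minus baseline | −1 | + / − | − / + | 0 of 4 | 0 of 4 |
| Improvement, baseline minus 8-week | +1 | + / + | − / − | 3 of 4 | 4 of 4 |
| MID achieved, yes/no | +1 | + / + | − / − | 3 of 4 | 4 of 4 |

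The composite, if aligned so that higher means more control, behaves like the control-type scales: it misses the criterion in the first two rows and meets it in the last two.

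**Simulation check**

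This used assumed path sizes and is illustrative only. The intervention shifts control by 0.3, 0.5 or 0.8 SD, paired with standardised control-to-interference effects of −0.3, −0.5 and −0.6. There is no direct effect, and catastrophizing is generated as the negative of control plus noise. With 40 participants, 20 per arm and no dropout, the chance that both sample correlations are positive, although the mechanism truly works, is:
- control-type scale, raw score: 0.00 to 0.02
- control-type scale, improvement: 0.81 to 0.995
- unreversed Pain Catastrophizing, raw score: 0.01 to 0.19
- unreversed Pain Catastrophizing, improvement: 0.00 to 0.01
- reversed Pain Catastrophizing, improvement: 0.77 to 0.99

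The pattern agrees with the table. The sign result does not depend on these path sizes.

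**The case against.** The strongest reply is that 11.2.3 leaves the coding open, so its direction is unstated rather than wrong. The Protocol Summary speaks of improvement and 11.2.2 uses MID achievement. With either coding the criterion is right for the three control-type scales and for the composite, which is the hypothesised mediator. A composite named for perceived control makes sense only if Pain Catastrophizing is reversed within it. The word positive may be loose wording for the hypothesised direction. The sentence sets no threshold and does not say that other patterns count against mediation. A sensible analyst who knows that benefit is a decrease would be unlikely to misread a negative correlation between control and pain interference. The criterion may also fit other outcomes, such as global impression of change or physical functioning, if higher means better there.

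Part of this stands. The point is confined to pain interference, the direction of Pain Catastrophizing is an assumption, and loose wording is possible. But the only scoring the plan gives for pain interference is a T-score with no reversal, and on that score the criterion fits nothing, whatever is assumed about Pain Catastrophizing. The favourable codings still leave the separate test of unreversed Pain Catastrophizing with two negatives. A positive correlation has a fixed meaning, and the section is headed as pre-specified. If the hypothesised direction was meant, the text should say so.

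**Conclusion.** The concern holds as a minor error in a stated criterion. With pain interference as a T-score or raw change, two positive correlations are the pattern of an unfavourable indirect path, and the criterion fits 0 of 4 component scales. With improvement or MID coding it fits 3 of 4. It fits all four only if the outcome is recoded in one of those ways and Pain Catastrophizing is also reversed; 11.2.3 states neither.

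The signs are expected signs. They assume that any direct effect of the intervention is zero or favourable, and that no confounding is large enough to reverse the mediator–outcome association. The 3-of-4 count also assumes that a higher Pain Catastrophizing score is worse; the 0-of-4 counts do not need that assumption.

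The consequence is limited to how an exploratory mechanism analysis is read, in a pilot that Section 11.1 says is not powered for significance. No primary or secondary endpoint result depends on it.

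**What to change.** Replace the criterion sentence in 11.2.3 with the expected sign of each path by scale and outcome, for example:

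> Evidence for a potential mediating effect will be associations in the hypothesised direction on both paths. For pain interference (T-score, lower = better), the expected signs for SOPA Control, Life Control, Meaning and Purpose and the composite are participation–mediator positive and mediator–outcome negative. For Pain Catastrophizing (unreversed, higher = worse) they are participation–mediator negative and mediator–outcome positive. Pain Catastrophizing is reverse-scored before it enters the composite.

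If improvement coding is intended, say so, and list + / + for the control-type scales and the composite and − / − for unreversed Pain Catastrophizing. Also state the scoring direction and expected signs for global impression of change and for any other outcome used in this analysis. Adjusting the mediator–outcome association for arm is an optional addition and not part of this correction.

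The cost is two or three sentences, with no new data and no change to any other analysis.

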3 STUDY DESIGN

3.1 Study Design

- NIH Behavioral Intervention Stage 1 randomized pilot trial to examine the acceptability and preliminary effects of the STEP-UP program on pain interference among older adults with chronic pain compared to a control group.
- Participants will be allocated into the two study arms in a 1:1 ratio by block randomization with mixed block sizes.

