11 STATISTICAL CONSIDERATIONS

11.1 Sample Size

This pilot study is not powered to determine the statistical significance of effects.

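### The mediation rule in Section 11.2.3 counts the sign of two sample correlations as evidence, and a program with no effect would often satisfy it by chance

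*Combined protocol and SAP*

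**What the plan says.** Section 11.2.3 opens by giving the purpose: "To explore potential mechanisms, we will examine the association between" two pairs of quantities. The first pair is "participation in the intervention and the hypothesized composite mediator, Perceived Control Over Pain", "as well as each of the 4 component scales". The second is the association "between mediators and outcomes". The criterion follows: "Positive correlations in both cases will provide evidence for a potential mediating effect".

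The section gives no minimum correlation, significance level, confidence interval, indirect-effect estimate or rule for multiple mediators. None appears elsewhere in Section 11 either. Section 11.1 says only that "This pilot study is not powered to determine the statistical significance of effects". The planned size is 40 people (Protocol Summary), allocated 1:1 (Section 3.1).

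**The concern.** Read as written, the criterion depends on sign alone: a correlation of 0.02 counts the same as one of 0.50. A sample correlation is almost never exactly zero, so when the true value is zero it falls on the positive side about half the time. The mediator-outcome leg may not help much. Scales chosen because they plausibly relate to pain may well correlate with pain outcomes whether or not the program changes them.

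At stake is the mechanism statement. Exploring mechanisms is part of the second aim (Section 1.3), and this analysis sits under a heading for pre-specified analyses, so its result is likely to be reported. A pre-specified criterion that a program with no effect meets so often cannot support the word evidence, even in a hedged sentence.

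**Working it through.** The plan states no error rate for this rule, so there is no figure to reproduce.

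**Inputs from the documents.** 40 people, 1:1, hence 20 per arm; one composite and four component scales; positive correlations required on both legs.

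**Assumptions, not in the documents.** Participation means assigned arm. All scales are scored in the direction of benefit. The composite is the mean of the components. One outcome is used. The program affects neither mediator nor outcome. The correlation among component scales is 0.3, 0.5 or 0.7. The mediator-outcome correlation (composite with outcome) runs from 0 to 0.4.

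**Step 1: participation leg, composite.** The arm-mediator correlation has the sign of the difference in arm means. With equal arms and no effect, that difference is symmetric about zero, so P(r > 0) = 0.5, less half the chance of an exact tie. Simulation gave 0.499 at 20/20, 0.500 at 16/16 and 0.499 at 18/14. A coarse, skewed score with 5.2% ties gave 0.475. Sample size and SD do not matter.

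**Step 2: participation leg, at least one of four components.** At inter-scale correlation 0.5 the exact value is 1 − 1/5 = 0.80, and simulation agrees. At 0.3 it is 0.86 and at 0.7 it is 0.73. If the scales were independent it would be 1 − 0.5⁴ = 0.94. Adding the composite changes nothing, because a mean above zero requires at least one component above zero.

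**Step 3: both legs, composite.** Swapping the arm labels reverses the first leg and leaves the second unchanged. Hence P(both) = 0.5 × P(second leg positive).

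| Mediator-outcome correlation | P(second leg > 0), n = 40 | P(both) |
|---|---|---|
| 0 | 0.50 | 0.25 |
| 0.2 | 0.90 | 0.45 |
| 0.3 | 0.97 | 0.49 |
| 0.4 | 0.995 | 0.50 |

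**Step 4: both legs, at least one component** (simulation; repeat runs differ by about one percentage point).

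| Inter-scale correlation | Mediator-outcome correlation 0 | Mediator-outcome correlation 0.4 |
|---|---|---|
| 0.3 | 60% | 85% |
| 0.5 | 55% | 80% |
| 0.7 | 48% | 73% |

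**Step 5: how much a positive sign tells us.** For an assumed true standardized arm difference of 0.5, P(r > 0) = Φ(0.5/√(2/20)) = Φ(1.58) = 0.94. Set against 0.50 under no effect, the likelihood ratio for the first leg is 0.94/0.50 = 1.9. It cannot exceed 1/0.5 = 2 however large the true effect is.

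**The case against.** The strongest reply is that the sentence was never meant as a pass/fail rule. The paragraph is framed as exploration, the effect is called potential, no decision depends on it, and Section 11.1 disclaims significance. The sentence may simply state the direction the team expects, and a team might apply a test by habit. This lowers the weight of the point but does not remove it. The text says what will count as evidence, and nothing in Section 11 narrows it.

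Some stronger readings are not supported:

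- **That the whole rule is met half the time whatever the data.** Both legs must be positive. The composite figure falls to 25% if mediator and outcome are unrelated, and no document gives that correlation.
- **That there are five separate chances.** With a composite formed as the mean of aligned components, there are in effect four, and they are correlated.
- **That one positive component would be declared a success, or that the result will shape a later trial.** The plan says neither. Its remark about a larger trial (Section 2) concerns the satisfaction items.

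It is also fair to object that participation could mean attendance, since the next paragraph of Section 11.2.3 discusses levels of session completion. Assigned arm is the more natural reading. Under the other, randomization no longer fixes the chance rate at one half, and it could be higher or lower.

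Finally, requiring significance would be a poor replacement. With 20 per arm, power at the two-sided 5% level for an assumed standardized difference of 0.5 is about 34%, 43% or 58% at baseline correlations of 0, 0.5 or 0.7. Real mechanisms would often fail such a test. That objection is accepted and is reflected in the change proposed.

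**Conclusion.** The point holds as a defect in the stated criterion for an exploratory analysis. Under the assumptions listed, a program with no effect meets the participation leg 50% of the time for the composite and 73% to 86% for at least one component. It meets the full rule 25% to 50% of the time for the composite. For at least one component the full rule is met about 48% to 60% of the time when mediator and outcome are uncorrelated, and 73% to 85% when they correlate 0.4.

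The 50% rests on randomization and symmetry alone. The other figures depend on assumed correlations and should be read as ranges. A reader might infer that the trial's main conclusions are at risk. They are not, because the primary and secondary analyses in Section 11.2.2 do not use this rule. What should change is what the trial may say about mechanism.

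**What to change.** Delete the sentence "Positive correlations in both cases will provide evidence for a potential mediating effect" from Section 11.2.3 and replace it with the following plan:

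- Define participation as assigned arm. Estimate the arm difference in the 8-week composite with the Section 11.2.2 model (baseline value as covariate), with a 95% CI.
- Estimate the mediator-outcome association adjusted for arm, with a 95% CI.
- Report the same two estimates for each of the four component scales as descriptive results.
- State that a positive sign alone is not evidence of mediation. Describe a leg as inconclusive when its interval includes no effect, without turning significance into a pass/fail gate.

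The cost is a few lines of text and code. No new data are needed, since Section 7.1 schedules all four scales at baseline and 8 weeks. The price is fewer and more cautious mechanism statements. With 20 per arm and no gain from baseline adjustment, the 95% interval for a mean difference extends about 1.96 × √(2/20) = 0.62 SD either side, so many results will be inconclusive.
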